Covid-19 related death will be defined as death within 30 days after PCR positive test for SARS-CoV-2. While this definition will allow us to assess the outcome contemporarily (i.e. no lag time) and is an epidemiological standard measure of infection-related mortality, a limitation to this approach is that it does not include covid-19 related death later than 30 days and may include deaths not specifically related to severe covid-19. Potential bias from these limitations, however, are mitigated by use of the comparative design (in which, we would not expect the risk of potential misclassification to be different between comparative groups). Some countries may be able to supplement with information from cause-of-death registers, but the inclusion of this information will be subject to availability.

In secondary analyses, all outcomes will be sub classified according to SARS-CoV-2 variants of concern using either a "periods of dominance"-approach where for each country we have identified the periods where specific variants dominated or, subject to data availability, variant-PCR and WGS results – see subsection *Intended additional analyses* below.

Through use of the planned outcomes, we will be able to provide information on the VE in relation to any SARS-CoV-2 infection as well as severe covid-19. In addition, variant-specific secondary analyses will provide information on VE according to specific variants of concern. The Nordic health care registers do not hold information to distinguish between symptomatic and asymptomatic documented SARS-CoV-2 infection.

COVARIATES

We will take the following potential confounders into account: age (using year of birth), sex, calendar month (of vaccination; ie, the index date) and vaccination priority group (nursing

home residents, healthcare personnel and individuals at risk of severe covid-19 due to comorbidities).

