	Denmark	The Danish Vaccination Register. Defined by the date where the respective vaccine dose examined was administered (i.e. 2nd or 3rd dose) and grouped into monthly intervals according to months since start of study period.	
Calendar month	Finland	The National Vaccination Register. Defined by the date where the respective vaccine dose examined was administered (i.e. 2nd or 3rd dose) and grouped into monthly intervals according to months since start of study period.	Categorical (14 levels): calendar month 1 (27 December 2020 to 31 January 2021) to month 14 (February 2022)
	Norway	The Norwegian Immunisation Register (SYSVAK). Defined by the date where the respective vaccine dose examined was administered (i.e. 2nd or 3rd dose) and	

		grouped into monthly intervals according to months since start of study period. The National Vaccination Register. Defined by the date where the respective	
	Sweden	vaccine dose examined was administered (i.e. 2nd or 3rd dose) and grouped into monthly intervals according to months since start of study period.	
	Denmark	The Danish Vaccination Register. Defined as governmentally assigned covid-19 vaccine priority groups, prioritized according to the risk of severe infection as well as whether being health and social care workers (assigned before first covid-19 vaccination).	Categorical (4 levels): Target risk groups, healthcare personnel, selected relatives of people at high risk, others
Covid-19 vaccine priority groups	Finland	Register of Social Assistance. Vulnerable individuals defined as individuals in 24-hours care (binary status per 27 December 2020). Social and Healthcare Professionals Register. Healthcare personnel defined as individuals with the right to act as health care personnel.	Categorical (3 levels): Vulnerable individuals, healthcare personnel, others
	Norway	The Norwegian Information System for the Nursing and Care Sector. Vulnerable individuals defined as nursing home resident (binary status per 27 December 2020). State register of employers and employees. Healthcare personnel defined as binary status per 27 December 2020.	Categorical (3 levels): Vulnerable individuals, healthcare personnel, others
	Sweden	Register on persons in nursing homes.	Categorical (3 levels): Vulnerable individuals,

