At the day an individual receives a 3. dose (i.e. the index date) of the studied schedule, the individuals will be matched with an individual having received the respective 2-dose comparison schedule (i.e. controls) but have not yet received a 3. dose (i.e. at the this date). For each matched pair, the index date of the individual in the 3-dose studied schedule will be assigned to the 2-dose comparison schedule control individual. The matched controls will be eligible to be included in a 3-dose studied schedule group in case of receiving a future 3. dose to that of the given matched date. Individuals from the 3-dose studied and the 2-dose comparison schedules will be matched on age (5-year bins), calendar month of receiving the 2. dose and a propensity score summarizing potential confounders such as sex, vaccination priority group and comorbidity. The time at which an individual was vaccinated with a 2. dose, is highly correlated with risk of severe covid-19 and/or risk behavior due to the national prioritization of the rollout of the covid-19 vaccines (e.g. individuals of high risk of severe covid-19 and health care workers were prioritized for earlier vaccination than the general public).

Individuals in the country-specific cohorts will be followed from the time they enter one of the vaccination schedules groups and 13 days have passed until one of the endpoints included in the study, end of endpoint ascertainment period, received a booster dose (a 3. dose for 2-dose schedules and a 4. dose for 3-dose schedules), exit from the cohort due to death, loss to follow-up, emigration, or end of study period, whichever occurs first. I.e. for the 3- vs. 2-dose matched comparisons, follow-up for the matched pairs will also end if the control individual receives a 3. dose (on that date; see example in Figure 4B). Follow-up will be conducted separately for each outcome without censoring for the other study outcomes. That is, when evaluating effectiveness against covid-19 hospitalization to an ICU, having a positive PCR test for SARS-CoV-2 or being covid-19 hospitalized does not right-censor the follow-up for this individual. However, note that when the 14 days and 30 days, respectively, after a positive test has passed, the follow-up will be censored in the analyses of hospitalization and ICU, and mortality, respectively.

[figure not shown]

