Quality control analysis: 3- vs. 2-dose schedule comparisons using a test-negative case-control study design

As an additional quality control, we will apply a test-negative case-control study design as previously done(19,21) to estimate VE against infection (positive PCR test SARS-CoV-2) in 3-vs 2-dose schedule comparisons. The results of these analyses will be compared to the corresponding comparison results from our main analysis. This will inform us on the possible impact of selection bias arising from differences in who is being tested.

Data on all (positive or negative) test results for the period 27 December 2020 to 28 February 2022 will be extracted for those aged 18 years or older (as of 27 December 2020). We will exclude any negative PCR test results taken within 3 days of a previous negative test result (as these results likely represent the same episode), negative test results taken within 21 days before a positive test result (as these are likely to be false negative), and positive and negative test results within 90 days of a previous positive test result. Since we will be evaluating the effectiveness of a 3. dose, only PCR tests taken from the date where the booster doses rollout started, specific for each country (i.e. in Denmark: 6 September 2021 [week 37, 2021]), will be retained for analysis. Participants will contribute with only one randomly chosen negative test result in the follow-up period. The 3. (booster) doses will be identified after this date and there must be at least 6 months (from 6 September 2021 to 13 December 2021 - subject for country-specific variation) or 4.5 months (from 14 December 2021 to 28 February 2022) between the 2. and 3. dose or from 2. dose and onset (i.e. of covid-19 related event). These time periods of "since 2. dose" denotes whether an individuals is eligible of receiving a 3. dose as per national-specific health authority guidelines on booster vaccination rollout. The effectiveness of a 3. dose from day 14 to day 28 (after the index date) will be compared with 2. dose schedules with onsets of events after at least the abovementioned 6 or 4.5 months eligibility criterion as well as to the immediate short period after the booster dose (i.e. the first 2-6 days; day 0 and 1 will not be included due to the potential risk of bias related to any testing due to initial reactogenicity).

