VE (1 – the odds of vaccination in cases divided by the odds of vaccination in controls) will be estimated using logistic regression (the PCR test result as the dependent variable); cases will

be those testing positive and controls will be those testing negative. The logistic regression models will be adjusted for age, sex, calendar month, vaccine priority group and comorbidity similar to the main analysis.

Please note that country participation for this sensitivity analysis will likewise be subject to the usability of each national booster vaccination rollout strategies to implement this design as well as the availability of dates of negative tests.

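### The test-negative quality-control model inherits a calendar month defined by vaccination date, so the date of the test is not controlled

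*Protocol*

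**What the plan says.** Protocol section 9.8 plans a test-negative case-control analysis of the 3- versus 2-dose comparisons for the infection endpoint. Its result is to be set against the main analysis, to show how far selection into testing may matter. On covariates it says: "The logistic regression models will be adjusted for age, sex, calendar month, vaccine priority group and comorbidity similar to the main analysis". It does not say which date the month refers to.

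The definitions elsewhere are all vaccination dates:

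- Section 9.3, covariate text: "calendar month (of vaccination; ie, the index date".
- Section 9.3, variable table, for all four countries: "Defined by the date where the respective vaccine dose examined was administered (i.e. 2nd or 3rd dose".
- Section 9.7, matching for the 3- versus 2-dose cohort: "calendar month of receiving the 2. dose and a propensity score summarizing potential confounders".

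The date of the test is not named as an adjustment variable anywhere.

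The design pools tests over the whole booster period. It keeps "only PCR tests taken from the date where the booster doses rollout started, specific for each country" (6 September 2021 in Denmark) and runs to 28 February 2022. On time since the second dose, "there must be at least 6 months (from 6 September 2021 to 13 December 2021" applies to the first part, and 4.5 months from 14 December 2021. Boosted tests count from day 14 to day 28 after the third dose. On controls: "Participants will contribute with only one randomly chosen negative test result in the follow-up period".

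**The concern.** Both test positivity and booster coverage can change sharply between September 2021 and February 2022. By the protocol's own variant periods (section 9.7), that span covers the move from Delta to Omicron. The date of the test is then an obvious confounder of a comparison of boosted with 2-dose tests.

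The main 3- versus 2-dose cohort deals with this by design, because "the index date of the individual in the 3-dose studied schedule will be assigned to the 2-dose comparison schedule control individual", so both members of a pair are followed over the same calendar days. The test-negative analysis is unmatched and draws each person's negative test at random over the period. Only a model term can align test dates, and the term the protocol supplies is a vaccination date.

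At stake is the reading of the check. If the test-negative VE differs from the cohort VE because of calendar time, the difference could be taken as evidence of testing bias in the main result. A calendar artefact could equally hide such bias. Section 9.6 has each country run its own analysis, so the four teams could also code the variable differently.

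**Working it through.** The protocol gives no figure for this analysis, so there is nothing to reproduce. The check is date arithmetic on the section 9.8 rules, using the Danish dates and taking 4.5 months as 137 days.

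**Reading A: month of the dose examined (section 9.3).** For a 2-dose test the relevant dose is the second; for a boosted test it is the third.

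1. Latest second dose that can yield a 2-dose test: 28 Feb 2022 − 137 days = 14 Oct 2021.
2. Earliest third dose: 6 Sep 2021.
3. So only the September and October 2021 dose months can contain both groups. With month indicators in the model, a month holding one group says nothing about the contrast between groups, so the booster odds ratio comes from these two months.
4. The 6-month rule cannot add earlier 2-dose tests here: 1 Sep 2021 plus 6 months is after the study end.

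| Dose month | Boosted tests (dose 3 + 14 to 28 days) | 2-dose tests (dose 2 + at least 137 days) |
|---|---|---|
| Sep 2021 | 6 Sep + 14 = 20 Sep, to 30 Sep + 28 = 28 Oct 2021 | 1 Sep + 137 = 16 Jan, to 28 Feb 2022 |
| Oct 2021 | 1 Oct + 14 = 15 Oct, to 31 Oct + 28 = 28 Nov 2021 | 1 Oct + 137 = 15 Feb, to 28 Feb 2022 |

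The two columns share no test date. The Omicron periods in section 9.7 start on 28 December 2021 (Denmark), 1 January 2022 (Finland and Norway) and 3 January 2022 (Sweden). All boosted tests in the table precede these dates and all 2-dose tests follow them.

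**Size under reading A with no true booster effect.** Apparent VE = 1 − [p1/(1 − p1)] / [p2/(1 − p2)], with p1 the positivity in the boosted window and p2 in the 2-dose window. The protocol gives no positivity, so these values are assumptions.

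- 10% and 20%: 1 − 0.1111/0.2500 = 1 − 0.444, about 56%.
- 5% and 30%: 1 − 0.0526/0.4286 = 1 − 0.123, about 88%.
- Equal positivity: 0%, no bias.

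**Reading B: month of the second dose for both groups (section 9.7).** The separation goes. For example, 2-dose tests after a May 2021 second dose can run from 31 October 2021 to 28 February 2022, and boosted tests from the same month fall in that span. Test date can still differ between groups within a second-dose month.

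**Simulation.** I assumed a true VE of 50%, Delta positivity of 5%, and assumed distributions of vaccination and test dates.

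| Omicron positivity | VE, month of dose examined | VE, month of dose 2 | VE, week of test |
|---|---|---|---|
| 5% | 47% | 49% | 48% |
| 10% | 77% | 47% | 49% |
| 20% | 89% | 46% | 50% |
| 30% | 94% | 46% | 50% |

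Month of test gave 48% to 51%. A second simulation, with a true VE of 0% and positivity rising from about 3.5% to about 29% under different assumed uptake curves, gave odds ratios of 0.10 (dose examined), 1.41 (dose 2) and 1.00 (week of test). Both simulations agree on readings A and test week. They differ greatly on the size of the bias under reading B.

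**The case against.** The strongest reply is that section 9.8 never says month of vaccination. Where the protocol means a dose month in an adjustment or matching list, it often says so, as section 9.7 does for both designs. Here the word stands bare, and in a model whose unit is a PCR test the month of the test is a natural intention. The reference to the main analysis may only mean a similar list of covariates. This stands as far as intention goes. It does not supply a definition: every one the protocol writes down is a vaccination date.

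A reader might infer that the analysis as written must compare Delta-era boosted tests with Omicron-era 2-dose tests. The document does not support that much. The contrast needs the second-dose month for one group and the third-dose month for the other. The section 9.3 wording gives that coding, but the corresponding 3- versus 2-dose main design uses second-dose month for both groups, and there the complete separation does not arise. Nor is a large spurious harm established under that reading, since its size rests on assumed curves.

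A reader might also infer that the whole check fails. Section 9.8 has a second comparator, days 2 to 6 after the booster. Both windows lie within 28 days of the same dose, so that contrast is largely unaffected.

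Three further limits are fair. The date windows are Danish, and section 9.8 allows rollout dates and intervals to vary by country. The section says the design follows earlier published work, which was not consulted. A statistical analysis plan may exist and was not seen. Covariate coding is often left to such a plan, but here the protocol itself names and defines the variable and carries it into a design where that definition does not fit.

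**Conclusion.** The point holds in a conditional form. The test-negative model adjusts for a calendar month that the protocol defines only by vaccination date, and nothing else in that unmatched design controls the date of the test. Under the section 9.3 definition and the Danish dates, the 3- versus 2-dose odds ratio is fully confounded with calendar time. That follows from the dates alone. How large the error would be depends on positivity: a null effect would look like a VE of about 56% at 10% versus 20%, or about 88% at 5% versus 30%. Under the section 9.7 second-dose month, a residual bias is possible, but its size depends on assumptions that the protocol cannot settle.

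This concerns one contrast in a quality-control analysis. It does not show bias in the main 3- versus 2-dose estimates, which are protected by the shared index date. The harm would be a misleading check on them.

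**What to change.** In section 9.8, replace calendar month in the test-negative model with calendar week (or month) of the PCR sample date, entered as a categorical term. State that the month of the examined dose is not used in this model. If second-dose timing is wanted as a marker of prioritisation, add the month of the second dose for both groups alongside the test-date term.

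The cost is one sentence and one covariate change in each country's code. From 6 September 2021 to 28 February 2022 is 176 days, so weekly categories add about 25 parameters and monthly categories 5. The sample dates are already needed for the section's own exclusion rules on repeat tests, so no new data are required.

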9.9 Limitations of the research methods

Although, the planned comparative design mitigates potential bias in recording of healthcare information between vaccinated and unvaccinated, there are some potential limitations to the chosen methodological approach. First, our ascertainment of the study outcomes is dependent on secondary use of national microbiology test results. Depending on the country and period, we will not have complete registration of all infected in the population; only those tested positive. Second, we do not have information on symptoms for our PCR positive cases; thus, this outcome may contain both asymptomatic and symptomatic cases. Third, as noted in the 'Variables' subsection, our outcomes for severe covid-19 (hospitalization, ICU admission and covid-19 related death) may potentially capture individuals with an outcome not directly related to covid-19 but where covid-19 was a contributing factor or co-occurred. Fourth, while the study design has a high degree of generalizability to similar general populations, some clinical subgroups will not be studied, including: individuals who have received an Ad26.CoV2-S (Johnson & Johnson vaccine), as why the results will not directly help inform on the comparative VE for these situations. Similarly, the proposed study objectives do not include analysis on high-risk subgroups such as individuals with immunocompromised conditions. Fifth, our planned methodology, weighting (for the specified design to address objective #1) and matching (for the specified design to address objective #2) both have strengths and limitations. Advantages of weighting (as opposed to matching) is the potential of preserving a large majority of the total study sample and allowing the assessment of several treatment effects (i.e. average treatment effect for the whole population, ATE). A limitation to this approach is that in case of poor overlap of covariates distribution across comparative groups, this will lower statistical power. Matching has the advantages of providing a 1:1 comparison with intuitive estimates of average treatment effect in the treated (ATT), but limitations to this approach is the discarding of unmatched individuals, which reduces the sample size and generally does not allow for multiple comparisons. A final limitation is that many schedules are strongly correlated with calendar period. Since calendar period is also strongly correlated with variant dominance, the results of many of the schedule comparisons will be variant-specific.

10. PROTECTION OF HUMAN PARTICIPANTS

No individual-level data will be shared between parties. Country-specific analyses are conducted on pseudo-anonymised data. All parties adhere to GDPR.

11. MANAGEMENT AND REPORTING OF ADVERSE EVENTS/ADVERSE REACTIONS

Not applicable. Secondary use of data.

12. PLANS FOR DISSEMINATING AND COMMUNICATING STUDY RESULTS

Main results expected in the final study report:

Table 1 will comprise the number of individuals (N[%]) in each country (columns) contributing follow-up in each vaccination schedule under study (rows).

Figure 1 will be a panel of forest plots – one for each schedule comparison. In each single schedule comparison forest plot, the combined VE estimates for each of the four study outcomes will be presented.

Table 2A will present combined VE estimates for the study outcome of PCR positive test for selected schedules according to a) waning of immunity, b) variants, c) age strata and d) vaccination priority group.

Table 2B will present combined VE estimates for the study outcome of covid-19 hospitalization for selected schedules according to a) waning of immunity, b) variants, c) age strata and d) vaccination priority group.

Table 2C will present combined VE estimates for the study outcome of all-cause mortality for selected schedules according to a) waning of immunity, b) variants, c) age strata and d) vaccination priority group.

The country-specific results underlying the combined effect estimates in Figure 1 and Tables 1-2C will be presented in table form in a supplementary appendix.

We anticipate multiple manuscripts.

We will adhere to the STROBE and ENCEPP guidelines when reporting results and drafting the manuscript(s).

Example of tables of results (2A-2C):

	Stud	ied	Comparative				
	sched	lule	scheo	dule	RR	RD	CVE
Outcome: X	Events	PYRS	Events	PYRS	(95% CI)	(95% CI)	(95% CI)
Comparison #1							
(eg, AZD1BNT2 vs							
BNT1BNT2)							
Waning of immunity							
(time since index							
date)							
120 days							
150 days							
180 days							
210 days							
240 days							
270 days							
300 days							
330 days							
360 days							
Age strata (years)							
18-40							
40-59							
60-74							
75+							
Vaccination priority							
group							
Vulnerable/high risk							
individuals							
Health care workers							
Others							
Comparison #2							
Etc.							

This Checklist should be included as an Annex by marketing authorisation holders when submitting the protocol of a non-interventional post-authorisation safety study (PASS) to a regulatory authority (see the Guidance on the format and content of the protocol of non-interventional post-authorisation safety studies). The Checklist is a supporting document and does not replace the format of the protocol for PASS presented in the Guidance and Module VIII of the Good pharmacovigilance practices (GVP).

Study title: Comparative effectiveness of heterologous and homologous primaryand booster SARS-CoV-2 vaccination schedules in the Nordic countries

EU PAS Register[®] number: Study reference number (if applicable):

Sect	ion 1: Milestones	Yes	No	N/A	Section Number
1.1	Does the protocol specify timelines for				6
	1.1.1 Start of data collection ¹	\bowtie			
	1.1.2 End of data collection ²	\bowtie			
	1.1.3 Progress report(s)		\boxtimes		
	1.1.4 Interim report(s)		\boxtimes		
	1.1.5 Registration in the EU PAS Register $^{\scriptscriptstyle(\!R\!)}$	\boxtimes			
	1.1.6 Final report of study results.	\square			

¹ Date from which information on the first study is first recorded in the study dataset or, in the case of secondary use of data, the date from which data extraction starts.

² Date from which the analytical dataset is completely available.

Section
Number
7-8

Sec	ion 3: Study design	Yes	No	N/A	Section Number
3.1	Is the study design described? (e.g. cohort, case- control, cross-sectional, other design)	\boxtimes			9
3.2	Does the protocol specify whether the study is based on primary, secondary or combined data collection?	\boxtimes			9
3.3	Does the protocol specify measures of occurrence? (e.g., rate, risk, prevalence)	\boxtimes			9
3.4	Does the protocol specify measure(s) of association? (e.g. risk, odds ratio, excess risk, rate ratio, hazard ratio, risk/rate difference, number needed to harm (NNH))	\boxtimes			9
3.5	Does the protocol describe the approach for the collection and reporting of adverse events/adverse reactions? (e.g. adverse events that will not be collected in case of primary data collection)	\boxtimes			11

Sect	ion 4: Source and study populations	Yes	No	N/A	Section Number
4.1	Is the source population described?	\square			9
4.2	Is the planned study population defined in terms of:				9
	4.2.1 Study time period	\square			
	4.2.2 Age and sex	\bowtie			
	4.2.3 Country of origin	\bowtie			
	4.2.4 Disease/indication	\boxtimes			

Section 4: Source and study populations	Yes	No	N/A	Section Number
4.2.5 Duration of follow-up	\square			9
4.3 Does the protocol define how the study population will be sampled from the source population? (e.g. event or inclusion/exclusion criteria)				9

Sect	ion 5: Exposure definition and measurement	Yes	No	N/A	Section Number
5.1	Does the protocol describe how the study exposure is defined and measured? (e.g. operational details for defining and categorising exposure, measurement of dose and duration of drug exposure)	\boxtimes			9
5.2	Does the protocol address the validity of the exposure measurement? (e.g. precision, accuracy, use of validation sub-study)		\boxtimes		
5.3	Is exposure categorised according to time windows?	\boxtimes			9
5.4	Is intensity of exposure addressed? (e.g. dose, duration)	\boxtimes			9
5.5	Is exposure categorised based on biological mechanism of action and taking into account the pharmacokinetics and pharmacodynamics of the drug?	\boxtimes			
5.6	Is (are) (an) appropriate comparator(s) identified?	\boxtimes			9

Sect	ion 6: Outcome definition and measurement	Yes	No	N/A	Section Number
6.1	Does the protocol specify the primary and secondary (if applicable) outcome(s) to be investigated?	\boxtimes			9
6.2	Does the protocol describe how the outcomes are defined and measured?	\boxtimes			9
6.3	Does the protocol address the validity of outcome measurement? (e.g. precision, accuracy, sensitivity, specificity, positive predictive value, use of validation sub- study)				9
6.4	Does the protocol describe specific outcomes relevant for Health Technology Assessment? (e.g. HRQoL, QALYS, DALYS, health care services utilisation, burden of disease or treatment, compliance, disease management)				

Sect	ion 7: Bias	Yes	No	N/A	Section Number
7.1	Does the protocol address ways to measure confounding? (e.g. confounding by indication)	\boxtimes			9
7.2	Does the protocol address selection bias? (e.g. healthy user/adherer bias)	\boxtimes			9
7.3	Does the protocol address information bias? (e.g. misclassification of exposure and outcomes, time-related bias)				9

Sec	tion 8: Effect measure modification	Yes	No	N/A	Section Number
8.1	Does the protocol address effect modifiers? (e.g. collection of data on known effect modifiers, sub-group analyses, anticipated direction of effect)	\boxtimes			9

Sect	ion 9: Data sources	Yes	No	N/A	Section Number
9.1	Does the protocol describe the data source(s) used in the study for the ascertainment of:				9
	9.1.1 Exposure? (e.g. pharmacy dispensing, general practice prescribing, claims data, self-report, face-to-face interview)	\boxtimes			
	9.1.2 Outcomes? (e.g. clinical records, laboratory markers or values, claims data, self-report, patient interview including scales and questionnaires, vital statistics)	\boxtimes			
	9.1.3 Covariates and other characteristics?	\square			
9.2	Does the protocol describe the information available from the data source(s) on:				9
	9.2.1 Exposure? (e.g. date of dispensing, drug quantity, dose, number of days of supply prescription, daily dosage, prescriber)	\boxtimes			
	9.2.2 Outcomes? (e.g. date of occurrence, multiple event, severity measures related to event)	\boxtimes			
	9.2.3 Covariates and other characteristics? (e.g. age, sex, clinical and drug use history, co-morbidity, co-medications, lifestyle)	\boxtimes			
9.3	Is a coding system described for:				9
	9.3.1 Exposure? (e.g. WHO Drug Dictionary, Anatomical Therapeutic Chemical (ATC) Classification System)	\square			
	9.3.2 Outcomes? (e.g. International Classification of Diseases (ICD), Medical Dictionary for Regulatory Activities (MedDRA))	\boxtimes			
	9.3.3 Covariates and other characteristics?	\boxtimes			
9.4	Is a linkage method between data sources described? (e.g. based on a unique identifier or other)	\boxtimes			9

Section 10: Analysis plan	Yes	No	N/A	Section Number
10.1 Are the statistical methods and the reason for their choice described?	\boxtimes			9
10.2 Is study size and/or statistical precision estimated?	\boxtimes			9
10.3 Are descriptive analyses included?				9
10.4 Are stratified analyses included?	\square			9
10.5 Does the plan describe methods for analytic control of confounding?	\boxtimes			9
10.6 Does the plan describe methods for analytic control of outcome misclassification?	\boxtimes			9
